9.2. Cumulative Dose

Cumulative dose will be calculated for AG-120, AG-221, and AZA, separately for Phase 1b and Phase 2. Cumulative dose is defined as the sum of all doses taken during the treatment period.

Cumulative dose for AG-120 and AG-221 in mg = Sum of (administered dose in mg during the treatment period); Cumulative dose for AZA in mg = Sum of (administered dose in mg during the treatment period); Cumulative dose for AZA in mg/m^2 = Sum of (prescribed dose in mg/m^2 during the treatment period);

The dosage will be counted as zero for days when the study drug is not taken.

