9.3. Dose Intensity

Dose intensity during the treatment is defined as the cumulative dose divided by the duration of treatment or modified duration of treatment. Dose intensity will be calculated in the following way:

Dose intensity for AG-120 and AG-221 = [cumulative dose in mg]/[duration of AG120/AG221 treatment (days)]. Duration of AG120/AG221 treatment (days) is defined as: (AG120/AG221 last dose date – AG120/AG221 first dose date + 1).

Dose intensity for AZA = [cumulative dose in mg/m²]/[modified duration of AZA treatment (days)]. Modified duration of AZA treatment (days) is defined as (start date of AZA last cycle – start date of AZA first cycle +28).

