9.4. Relative Dose Intensity

Relative dose intensity is the dose intensity divided by the planned dose intensity.

For Phase 1b, the planned dose intensity for AG-120 and AG-221 will vary by dose cohort.

For Phase 2, the planned dose intensity for AG-221 will be determined in Phase 1b.

For both Phase 1b and Phase 2, the planned dose for AZA is 75 mg/m²/day for 7 days of each 28-day treatment cycle, so the planned dose intensity is 18.75 mg/m²/day;

Relative dose intensity for all drugs mentioned above will be categorized into < 75%, 75% to < 90%, 90% to < 120%, and ≥120%, and frequency counts will be provided by dose cohort (Phase 1b) or treatment arm (Phase 2).

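### Azacitidine dose intensity and relative dose intensity are built on prescribed mg/m², so they do not register a difference between administered and prescribed dose on treated days

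*SAP*

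**What the plan says.** SAP 9.2 opens with a general rule: "Cumulative dose is defined as the sum of all doses taken during the treatment period". It then gives two azacitidine versions. In mg, the rule is followed: "Cumulative dose for AZA in mg = Sum of (administered dose in mg during the treatment period". In mg/m², the summand changes to the prescribed amount: "Sum of (prescribed dose in mg/m^2 during the treatment period". A closing line covers untreated days: "The dosage will be counted as zero for days when the study drug is not taken".

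SAP 9.3 takes the mg/m² version forward, "Dose intensity for AZA = [cumulative dose in mg/m²]/[modified duration of AZA treatment (days", with the denominator running as "start date of AZA last cycle – start date of AZA first cycle +28". For the oral drugs it uses the administered mg: "Dose intensity for AG-120 and AG-221 = [cumulative dose in mg]/[duration of AG120/AG221 treatment (days". SAP 9.4 divides each by the planned intensity and sorts all drugs into the same categories, with cut points at 75%, 90% and 120%.

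SAP 9.5 adds an average daily dose (cumulative mg over days dosed) and, for azacitidine, an average prescribed daily dose (cumulative mg/m² over days dosed). The opening of SAP 9 has all of these summarised by treatment arm in Phase 2, with subject listings.

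**The concern.** The mg/m² formula conflicts with the definition at the head of its own section. It also gives relative dose intensity two meanings in one set of tables: delivered against planned for AG-120 and AG-221, but prescribed against planned (on days when drug was given) for azacitidine.

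Azacitidine is common to both Phase 2 arms. Of the planned summaries, relative dose intensity is the one that is both scaled to body size and referenced to plan. A reader asking whether azacitidine was delivered equally well with and without AG-221 would look there first. On a treated day that summary assumes that what was prescribed was given, neither less nor more.

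**Working it through.** **Inputs.** From SAP 9.4, "the planned dose for AZA is 75 mg/m²/day for 7 days of each 28-day treatment cycle". From SAP 9.3, the modified duration quoted above. The delivered fraction f, a BSA of 1.8 m² and a course of six 28-day cycles are assumptions for illustration; the documents give no figure for f.

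**Step 1: the plan's own figure.** Planned intensity = 75 × 7 / 28 = 18.75 mg/m²/day. This reproduces SAP 9.4.

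**Step 2: full dosing under the SAP formula.** Prescribed sum = 6 × 7 × 75 = 3150 mg/m². Modified duration = 5 × 28 + 28 = 168 days. Dose intensity = 3150 / 168 = 18.75, so relative dose intensity (RDI) = 100%.

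**Step 3: partial delivery on treated days.** Let P be the prescribed sum, D the modified duration, and f the fraction of P actually given on treated days.

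- Reported RDI = P / (D × 18.75)
- True RDI = f × P / (D × 18.75)
- Hence reported RDI = true RDI / f

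| f (assumed) | Reported RDI | True RDI | Overstatement (1/f − 1) |
|---|---|---|---|
| 1.00 | 100% | 100% | 0% |
| 0.95 | 100% | 95% | 5.3% |
| 0.90 | 100% | 90% | 11.1% |
| 0.80 | 100% | 80% | 25.0% |

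The reported value stays at 100% in every row. With f above 1 the same formula understates delivery.

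**Step 4: what the SAP formula still captures.**

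- Missed days, 5 of 7 given in each cycle: 6 × 5 × 75 / 168 = 13.39; 13.39 / 18.75 = 71.4%.
- Prescribed reduction to 37.5 mg/m² throughout: 6 × 7 × 37.5 / 168 = 9.375; 9.375 / 18.75 = 50%.
- One 14-day delay before a later cycle: D = 168 + 14 = 182; 3150 / 182 = 17.31; 17.31 / 18.75 = 92.3%.

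**Step 5: what other by-arm summaries capture.** At BSA 1.8 m² and f = 0.80:

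- Administered cumulative dose falls from 3150 × 1.8 = 5670 mg to 5670 × 0.80 = 4536 mg.
- Average daily dose falls from 5670 / 42 = 135 mg to 4536 / 42 = 108 mg.
- Average prescribed daily dose stays at 3150 / 42 = 75 mg/m².

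**The case against.** The best case for leaving the formula alone has four parts.

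- The documented routes to lower azacitidine exposure are already visible. Cycle delays lengthen the denominator, reductions under Protocol 7.2.2.3.4 lower the prescribed dose, and missed days count as zero. Stopping azacitidine shows in duration and cycle counts (SAP 9.1) and in the single-drug discontinuation count (SAP 9.6), which also tabulates dose modifications with reasons.
- Partial dosing on a treated day is not described as a regular event. Site staff give azacitidine (Protocol 7.6), and the dose is set on Day 1 of each cycle and then held for that cycle (Protocol Table 4, footnote j).
- A shortfall of similar size in both arms would not distort the comparison between them.
- Nothing inferential depends on it. Exposure is summarised descriptively, the ORR test uses the ITT population with no exposure variable (SAP 10.1), and SAP 11 plans no inferential safety analysis.

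All four stand, and they limit the importance of the point. They do not remove the conflict inside SAP 9.2 or the different meaning of RDI across drugs. Nor is a mismatch between prescribed and given doses foreign to the protocol. Section 7.2 sets a 10% margin for SC overdose, and Appendix H splits doses above 100 mg between two syringes; at 75 mg/m² that applies to any BSA above 100 / 75 = 1.33 m². How often a mismatch occurs is not stated.

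A reader might infer that under-delivery disappears from the whole between-arm exposure comparison, or that an effect of AG-221 on azacitidine delivery would be hidden. The documents do not support either inference: Step 4 shows the main routes lowering RDI, and Step 5 shows the administered mg summaries falling with a partial dose. Those mg summaries are weaker because they depend on body size and have no planned value beside them, but they are not blind. The average calculated daily dose named at the start of SAP 9 is not defined in 9.1 to 9.6, so it cannot be counted on either way.

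**Conclusion.** The point holds in a limited form. As written, azacitidine dose intensity and RDI do not register any difference between administered and prescribed dose on days when drug was given, and this departs from the doses-taken definition in SAP 9.2 and from the treatment of AG-120 and AG-221. The average prescribed daily dose in SAP 9.5 has the same property, but it is correctly labelled and is not a fault.

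The size cannot be determined from the documents. The 0 to 5% and 11% overstatements rest wholly on the assumed f. It would also go too far to infer that subjects will be placed in the wrong RDI category: an f of 0.90 would report a true 85% as 85 / 0.90 = 94.4%, across the 90% cut, but nothing in the documents supports an average shortfall of that size. This is a minor correction to a descriptive summary and has no bearing on the primary test.

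**What to change.** For SAP 9.3 and 9.4, define cumulative azacitidine in mg/m² as the sum, over treated days, of administered mg divided by that cycle's Day 1 BSA. Use the BSA that the site used for dosing where it is recorded; otherwise calculate it from Day 1 weight and screening height with the formula in Protocol Table 4, footnote j. Keep the prescribed sum only for the average prescribed daily dose in 9.5, and name the two mg/m² sums differently.

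The cost is a change to one formula and minor reprogramming. Administered azacitidine mg is already summed under SAP 9.2, and Protocol Table 4 schedules weight on Day 1 of each cycle and height at screening, so no new data collection should be needed. The downside is small noise where a recalculated BSA differs from the one the site used; SAP 8.1 itself allows for BSA not being collected in the eCRF. A footnote saying which BSA was used would cover this.

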9.3. Dose Intensity

Dose intensity during the treatment is defined as the cumulative dose divided by the duration of treatment or modified duration of treatment. Dose intensity will be calculated in the following way:

Dose intensity for AG-120 and AG-221 = [cumulative dose in mg]/[duration of AG120/AG221 treatment (days)]. Duration of AG120/AG221 treatment (days) is defined as: (AG120/AG221 last dose date – AG120/AG221 first dose date + 1).

Dose intensity for AZA = [cumulative dose in mg/m²]/[modified duration of AZA treatment (days)]. Modified duration of AZA treatment (days) is defined as (start date of AZA last cycle – start date of AZA first cycle +28).

9.4. Relative Dose Intensity

Relative dose intensity is the dose intensity divided by the planned dose intensity.

For Phase 1b, the planned dose intensity for AG-120 and AG-221 will vary by dose cohort.

For Phase 2, the planned dose intensity for AG-221 will be determined in Phase 1b.

For both Phase 1b and Phase 2, the planned dose for AZA is 75 mg/m²/day for 7 days of each 28-day treatment cycle, so the planned dose intensity is 18.75 mg/m²/day;

Relative dose intensity for all drugs mentioned above will be categorized into < 75%, 75% to < 90%, 90% to < 120%, and ≥120%, and frequency counts will be provided by dose cohort (Phase 1b) or treatment arm (Phase 2).

9.5. Average Daily Dose and Average Prescribed Daily Dose for AZA

Average daily dose during treatment is defined as the cumulative dose in mg divided by number of days dosed. Average prescribed daily dose for AZA is defined as the cumulative dose in mg/m² divided by number of days dosed. A single average value will be computed for each subject, and then the descriptive statistics will be computed for each dose cohort (Phase 1b) or treatment arm (Phase 2).

9.6. Dose Modification

The number of subjects who have at least one dose modification (interruption/reduction), number of dose modifications per subject, and reasons for dose modifications will be summarized by dose cohort (Phase 1b) or treatment arm (Phase 2). Details of dose adjustments will be provided in a by subject listing.

The discontinuation of AG-120, AG-221, or AZA for subjects in the combination arms of the study is allowed. Subjects may continue treatment with single agent AG-120, AG-221, or AZA if in the investigator's assessment the subject continues to show clinical benefit and all protocol-specified criteria for continuing study treatment are met. Number of subjects who discontinue one drug (AG-120, AG-221 or AZA) in combined treatment arms of AG-120 + AZA or AG-221 + AZA will be summarized.

10. EFFICACY ANALYSIS

All efficacy analyses will be conducted separately for Phase 1b and Phase 2. All efficacy analysis will be performed on the FAP population (Phase 1b) and on the ITT population and mITT as well (Phase 2) unless otherwise specified. Key efficacy analyses will also be performed on EAP supportive evidence and to assess the robustness of the efficacy findings for both Phase 1b and Phase 2. Subjects will be analyzed according to either dose cohort (Phase 1b) or randomized treatment arm (Phase 2).

All statistical tests will be two-sided at the significance level of $\alpha=0.05$ unless otherwise specified, and the corresponding p-values and two-sided 95% confidence interval (CI) for intended point estimates will be reported, unless specified otherwise.

10.1. Analysis of Primary Efficacy Endpoint

Phase 1b does not have a primary efficacy endpoint.

For Phase 2, the primary efficacy endpoint of ORR is defined as rate of CR + CRi+ CRp + MLFS + PR according to modified IWG AML response criteria as assessed by investigator. The analysis of the primary endpoint ORR will be based on the ITT population. Subjects will be analyzed as they were randomized, regardless of the actual treatment received. The ORR will be summarized by treatment arm. The treatment difference in ORR will be tested using the Chi-squared test or Fisher exact test if appropriate at a two-sided 0.2 level and in the ITT population. This test will provide the pivotal p-value for the comparison of the ORR of the oral AG-221 + SC azacitidine versus azacitidine mono therapy. Estimated response rate with 80% and 95% CIs will also be provided.

Response will also be summarized by the best overall response following the hierarchical order of CR, CRi/CRp, PR, MLFS, stable disease (SD), progressive disease (PD)/relapse, and not evaluable (NE). Cytogenetic Complete Remission (CRc) will be counted as CR thus will not be summarized separately. The best response of CRi and CRp are of the same rank and thus will be reported as a single category. The best response of PD, and relapse, will be grouped together. Sensitivity analyses will be performed on the mITT and EAP.

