## Statistical Methods

### Phase 1b (Dose-finding and AG-120 Expansion) Stage:

Statistical analyses in Phase 1b will be primarily descriptive in nature. Tabulations will be produced for disposition, demographic and baseline disease characteristics, safety, PK, PD, and clinical activity parameters. Categorical data will be summarized by frequency distributions (numbers and percentages of subjects) and continuous data will be summarized by descriptive statistics (mean, standard deviation, median, minimum, and maximum). Data will be summarized by dose level and overall when appropriate.

[figure not shown]
Phase 2 AG-221 Randomized Stage:

[figure not shown]
The primary efficacy endpoint of Overall Response Rate (ORR) in Phase 2 includes responses of CR, CRp, CRi, morphologic leukemia-free state (MLFS), and PR, according to modified IWG AML response criteria. The treatment difference in ORR will be tested using the Chi square test in the ITT population. This test will provide the pivotal p-value for the comparison of the ORRs of oral AG-221 + SC azacitidine versus azacitidine mono therapy group.

Approximately 99 subjects will be randomized in this study with 66 IDH2 subjects in the oral AG-221 + SC azacitidine arm, and 33 IDH2 subjects in the SC azacitidine mono therapy arm. Assuming an ORR of 30% in the azacitidine mono therapy arm and an ORR of 50% for oral AG-221 + SC azacitidine arm this designed sample size (66 in the AG-221 + SC azacitidine and 33 in the azacitidine mono therapy arm) will provide 75% power to detect a 20% difference in ORR at a Type I error rate of 0.2 (two-sided).

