**7.2.2.2. Phase 2 AG-221 Randomization Stage**

Randomization occurs via IWRS after confirming ongoing eligibility of the subject. All subjects randomized will be stratified by primary (ie, de novo) or secondary (progression of MDS or myeloproliferative neoplasms [MPN], or therapy-related) AML according to the WHO classification ([Appendix B](#)).

Oral AG-221 + SC azacitidine treatment arm will be initiated at the RCD of AG-221 on Days 1 - 28 of each 28-day treatment cycle. Both combination and single agent azacitidine will be administered at 75 mg/m^2/day SC for 7 days of each 28-day cycle. Pending the outcome of the Phase 1b dose-finding, a dose escalation of AG-221 to 200 mg daily may be initiated to augment treatment response as stated in Section [7.2.2.3.1](#) below.

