##### **9.6.2. Phase 2 AG-221 Randomized Stage**

For subjects in Phase 2, response will be primarily assessed by investigator review.

All efficacy analysis will be performed in the ITT population. Key efficacy analysis will also be performed on the mITT and EAP as supportive evidence and to assess the robustness of the efficacy findings. Subjects will be analyzed according to randomized treatment group.

The primary efficacy endpoint ORR is defined as the rate of responses including CR, CRi, CRp, MLFS and PR that are assessed by investigator according to modified IWG AML response criteria. The ORR will be summarized by treatment group. The treatment difference in ORR will be tested using the Chi squared test at a two-side 0.2 level and in the ITT population. This test will provide the pivotal p-value for the comparison of the ORR of the oral AG-221 + SC azacitidine versus azacitidine mono therapy. Estimated response rate with 80% and 95% confidence intervals will also be provided.

**Event-free survival (EFS)** is defined as the interval from the date of randomization to the date of documented morphologic relapse, progression, or death from any cause, whichever occurs first. The analysis of the **EFS** will be conducted using the log-rank test in the ITT population. This test will be used for the comparison of the two EFS curves of oral AG-221+ SC azacitidine versus azacitidine mono therapy. The Cox proportional hazards regression model will be used to estimate the hazard ratio and a 95% confidence interval for the hazard ratio.

**Duration of response** is defined as time from the first documented CR/CRi/CRp/MLFS/PR to the date of the first documented morphologic relapse, progression according to modified IWG AML response criteria ([Appendix F](#)), or death due to any cause, whichever occurs first. Subjects without morphologic relapse, progression, or death due to any cause will be censored at the date of the last response assessment. Duration of response will be assessed using Kaplan-Meier methods. Point estimates and 95% CIs will be provided where appropriate for the median and other quantiles.

**Time to response** is defined as time from the date of first dose to the date of first occurrence of response, which includes CR, CRi, CRp, PR and MLFS as determined by investigator. Time to response will be summarized using descriptive statistics in subjects with documented CR, CRi, CRp, PR and MLFS as determined by the investigator.

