For **HRQoL** data, analyses will address the mean differences by treatment group on the EORTC QLQ-C30 scale and subscale scores and the treatment group differences in the proportion of subjects who achieve minimal clinically important differences. EQ-5D-5L will be scored according to the instrument guidance and analyzed accordingly.

Overall survival and one year survival rates will be analyzed using Kaplan-Meier method, and the treatment comparison will be conducted using log-rank test.

The other secondary endpoints include complete remission rate, best overall objective response rate, rate of hematologic improvement (HI), the sponsor assessed CR/CRh (based on laboratory dataset) and duration of CR/CRh. These endpoints will be analyzed using the statistical methods mentioned above or other statistical methods as appropriate. As noted, CRh is not available from the investigator assessment. As a result, the analyses on CR/CRh will be based on the sponsor derived assessment.

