4.3. Stratification, Randomization, and Blinding

Randomization only applies to the Phase 2 part and will be carried out using an Interactive Web Response System (IWRS). Subjects with an IDH2 mutation will be randomized to receive oral AG-221 + SC azacitidine (Arm 1) versus SC azacitidine (Arm 2) in 2:1 ratio. Arm 1 will include a minimum of 66 subjects and Arm 2 will include a minimum of 33 subjects, (99 subjects total in both arms).

For the Phase 2 part, all subjects randomized will be stratified by primary (i.e., de novo) or secondary (progression of MDS or myeloproliferative neoplasms [MPN], or therapy-related) AML according to the WHO classification.

During Phase 1b and Phase 2 a retrospective central pathology review of all bone marrow aspirates and/or biopsies and peripheral blood smears, which are collected in subjects of the AG-221 (Phase 1b dose-finding and Phase 2 randomized stage) treatment arms during screening, will be conducted by personnel blinded to subject treatment to confirm eligibility. Bone marrow aspirate and/or biopsy and peripheral blood smear collected after the start of study treatment must be available for both local and central pathology review. The retrospective central pathology review will require a set of duplicate slides for each bone marrow collection time point including bone marrow aspirate (BMA), peripheral blood smear, and bone marrow biopsy (BMB) if performed. The central pathology review will be conducted by personnel blinded to study treatment.

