10.2.1. Event-free survival

EFS is assessed by investigator based on modified International Working Group (IWG) AML response criteria (Section 17.4).

Event-free survival (EFS) is defined as the interval from either the date of the first dose for subjects in Phase 1b or the date of randomization for subjects in Phase 2 to the date of documented morphologic relapse, progression, or death from any cause, whichever occurs first. Censoring rules are provided in Table 4. The analysis of the EFS for Phase 2 will be conducted using the log-rank test in the ITT population, and mITT population. The Cox proportional hazards regression model will be used to estimate the hazard ratio and the corresponding 95% confidence interval for oral AG-221 with SC azacitidine relative to SC azacitidine alone.

Additionally, the number of events, the number of censored and reasons for censoring will be summarized (n, percent) for this endpoint. KM curves will be provided by treatment arm in figures.

Table 4: Censoring Rules for EFS

Value of Event-free Survival Date (ADT)	Censored (Y, N)	Derivation
ADT = min(death date, MR date, progression date)	N	If a subject died, had MR, or had disease progression by investigator review, and the subject has less than two consecutive missing response assessments prior to a visit documented death, MR, or progression which is before new AML therapy
ADT = the last event-free assessment date before missing assessments/ randomization date	Y	If a subject died, had MR, or had disease progression by investigator review, and the subject has two or more consecutive missing response assessments prior to a visit documented death, MR, or progression
ADT = the last adequate assessment date/randomization date	Y	If a subject did not die, did not have MR, or did not have progression, and did not receive any subsequent anticancer therapy. If there was no post-baseline response assessment, then ADT = the randomization date.
ADT = the last adequate assessment date on or prior to start of subsequent anticancer therapy/randomization date	Y	If a subject did not die, did not have MR, or did not have progression on or prior to start of subsequent anticancer therapy. If there was no post-baseline response assessment, then ADT = the randomization date.

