10.2.4. Overall Survival

Overall survival (OS) is defined as time from first date of study drug (Phase 1b) or randomization (Phase 2) to death due to any cause. This time to event endpoint will be analyzed, similarly to the EFS analyses described in 10.2.1. Sensitivity analysis for OS may be explored if needed.

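### Phase 2 is randomised within primary/secondary AML strata, but the ORR, EFS and OS comparisons are all planned without the stratum

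*SAP*

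**What the plan says.** **Design.** SAP 4.3 states that "all subjects randomized will be stratified by primary (i.e., de novo) or secondary (progression of MDS or myeloproliferative neoplasms [MPN], or therapy-related) AML". Protocol 7.2.2.2 names the same factor and adds that "Randomization occurs via IWRS after confirming ongoing eligibility of the subject", so the stratum is recorded at randomisation.

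**ORR.** The Protocol Summary (Statistical Methods) says "The treatment difference in ORR will be tested using the Chi square test in the ITT population". Protocol 9.6.2 says "The treatment difference in ORR will be tested using the Chi squared test at a two-side 0.2 level and in the ITT population". SAP 10.1 adds an alternative: "The treatment difference in ORR will be tested using the Chi-squared test or Fisher exact test if appropriate at a two-sided 0.2 level". None of the three mentions the stratum.

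**EFS and OS.** SAP 10.2.1 says "The analysis of the EFS for Phase 2 will be conducted using the log-rank test in the ITT population, and mITT population", followed by a Cox model with no strata or covariates named. Protocol 9.6.2 says "Overall survival and one year survival rates will be analyzed using Kaplan-Meier method, and the treatment comparison will be conducted using log-rank test", and SAP 10.2.4 says of OS "This time to event endpoint will be analyzed, similarly to the EFS analyses described in 10.2.1". The EFS sensitivity analyses at the end of SAP 10.2.1 change only the censoring rules.

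**Where the factor does appear.** In the efficacy analyses it is one of ten subgroups in SAP 10.3, which limits subgroup analysis to ORR and OS. The EFS analysis never uses it.

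**The concern.** A sponsor stratifies on a factor because it expects the factor to predict outcome. The protocol's amendment rationale for choosing this one refers to poorer prognosis and treatment resistance in secondary AML. Stratified allocation balances the arms on the factor, so variation between strata hardly contributes to the observed difference between arms. The unstratified variance still counts that variation. The test is then conservative, and some of the benefit of stratifying is lost. For time-to-event endpoints, the unstratified hazard ratio is also pulled towards 1 relative to the within-stratum one.

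The second, smaller matter is the Fisher alternative in SAP 10.1. It has no trigger, so the choice of test for the pivotal p-value is open.

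**Working it through.** **1. The plan's own figure.** Inputs from SAP 4.4: 66 versus 33 subjects, ORR 50% versus 30%, two-sided alpha 0.2 (z = 1.2816), stated power 75%.
- Unpooled SE: √(0.3·0.7/33 + 0.5·0.5/66) = 0.1008. Power = Φ(0.2/0.1008 − 1.2816) = 75.9%.
- Pooled null SE: with p̄ = (9.9 + 33)/99 = 0.4333, √(0.4333·0.5667·(1/33 + 1/66)) = 0.1056. Power = Φ((0.2 − 1.2816·0.1056)/0.1008) = 73.9%.
- Exact enumeration of all 34 × 67 outcomes: uncorrected chi-squared 75.3%, Fisher 69.7%, continuity-corrected chi-squared 66.2%.

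The stated 75% is therefore the power of an unstratified, uncorrected chi-squared test.

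**2. Why the unstratified test turns conservative.** Assume half the subjects have secondary AML, overall null ORR 30%, and a gap g between strata. The pooled variance 0.3·0.7 = 0.21 equals the within-stratum variance plus (g/2)². Only the within-stratum part drives the arm difference, so size ≈ 2·(1 − Φ(1.2816·√(0.21/(0.21 − g²/4)))).
- g = 20 points: within-stratum variance 0.20, size ≈ 0.189
- g = 30 points: 0.1875, size ≈ 0.175
- g = 40 points: 0.17, size ≈ 0.154

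The simulation below agrees with this.

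**3. ORR: chi-squared versus CMH.** The CMH statistic is (Σ[xᵢ − tᵢmᵢ/nᵢ])² / Σ[tᵢcᵢmᵢ(nᵢ − mᵢ)/(nᵢ²(nᵢ − 1))]. In stratum i, xᵢ is treated responders, mᵢ all responders, tᵢ and cᵢ the arm sizes, and nᵢ their total. Assumptions: permuted blocks of 6, half secondary AML, and an additive 20-point effect in both strata.

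| Control-ORR gap (points) | Size, chi-squared | Power, chi-squared | Power, CMH |
|---|---|---|---|
| 0 | 0.203 | 75.1% | 74.3% |
| 10 | 0.200 | 75.2% | 74.7% |
| 20 | 0.191 | 75.5% | 75.8% |
| 30 | 0.178 | 76.1% | 77.5% |
| 40 | 0.158 | 77.0% | 80.1% |

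CMH size stays at 0.200 to 0.201. Break-even is at a gap of 17 to 18 points. With 30% secondary AML, break-even is 18 to 19 points and the power change runs from −0.8 to +2.4 points.

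The result depends on the model. With a common odds ratio and stratum sizes held fixed (primary share 50% to 75%), CMH loses 0.9 to 1.3 points at no gap and is level to within 0.4 points at a 10-point gap. In that model it gains 0.7 to 1.3 points at 20, about 2 to 3 at 30, and 5 to 8 at 40 (shares 50% to 70%). With a common odds ratio and varying stratum sizes, break-even stays at about 16 to 19 points.

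**4. EFS and OS.** The documents give no event count, hazard ratio or stratum effect. Assumed: within-stratum HR 0.70, control median about 12 months, about 60 events, half secondary AML, alpha 0.05, and 20,000 simulated trials per setting (Monte Carlo SE about 0.3 points on power).

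| Stratum HR | Size, unstratified / stratified | Power, unstratified / stratified | Geometric mean HR, unstratified / stratified |
|---|---|---|---|
| 1 | 5.4% / 5.3% | 28.0% / 27.8% | 0.698 / 0.698 |
| 1.5 | 4.7% / 5.0% | 26.8% / 27.5% | 0.703 / 0.698 |
| 2 | 4.3% / 5.3% | 24.6% / 27.0% | 0.711 / 0.698 |
| 3 | 3.1% / 5.2% | 20.6% / 27.1% | 0.730 / 0.697 |

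Up to a stratum HR of 1.5 there is no clear difference.

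**5. Fisher or chi-squared.** At 50% versus 30% the two tests disagree in 5.7% of trials, always with chi-squared significant and Fisher not (75.3 − 69.7 = 5.6 with rounding). Fisher's actual size at a 30% null is 0.166 against the nominal 0.2. An expected-count rule would almost never call for Fisher. The smallest expected counts are in the control arm, at one third of total responders or non-responders, so fewer than 15 of 99 in one category would be needed. The design expects 42.9 responders. The probability that the tests disagree and an expected count is below 5 is 1.4 × 10⁻¹¹. The loss therefore arises only if Fisher is chosen for some other reason.

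**The case against.** The strongest reply is that nothing here is wrong. Chi-squared is the protocol's pre-specified test, its 75% power is right, and type I error is controlled. For gaps of 0 to 20 points, CMH changes power by about −0.8 to +0.3 points in the additive model. A material gain needs a gap of 30 to 40 points, and neither document gives a stratum ORR. The EFS and OS figures rest entirely on assumed inputs. SAP 10.3 already gives stratum-specific estimates for ORR and OS, and SAP 10.2 qualifies the log-rank p-value loosely enough not to forbid strata. The protocol's Justification for Amendment also reports that the primary-analysis CSR (data cutoff 19 Aug 2019) was finalised, so changing the pivotal test may no longer be open.

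Most of this stands, and it limits the point to an inexpensive improvement. It does not remove it. A subgroup forest plot is not a stratified treatment comparison, and EFS has not even that. A qualifier that permits stratification does not pre-specify it. The timing argument affects which remedy is used, not whether the omission exists.

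On Fisher, SAP 10.2.7, 10.2.10 and 10.2.11 prescribe it outright for secondary rates, although SAP 10.2 says such rates are handled like ORR. SAP 8 also assigns Fisher to binary baseline variables. Those passages are a separate inconsistency. They make an undefined option in the pivotal test more likely to be read as Fisher.

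**Conclusion.** The concern holds. The randomisation factor is absent from the ORR, EFS and OS treatment comparisons. The cost is efficiency and consistency with the design, not validity.

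For ORR, stratifying costs about 1 point of power if the factor is not prognostic. At a 40-point control gap it gains about 2 to 3 points under an additive effect and up to about 8 under a common odds ratio. Break-even is at about 16 to 19 points when stratum sizes vary, and nearer 10 in some settings with sizes held fixed. For EFS and OS the gain is negligible up to a stratum HR of 1.5 and clear at 2 to 3, under the assumed event count and hazard ratio. Stratum share, stratum effect and block size are all assumptions.

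The Fisher option can only lose significance relative to chi-squared. It would cut power by about 5.6 points if used without a sparse-data reason.

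**What to change.** **If the pivotal test can still be changed,** amend both documents together.
- ORR (Protocol Summary, Protocol 9.6.2, SAP 10.1): CMH stratified by the IWRS factor at two-sided 0.2, with a Mantel-Haenszel risk difference and 80% and 95% CIs.
- EFS and OS (Protocol 9.6.2; SAP 10.2, 10.2.1, 10.2.4): stratified log-rank and stratified Cox.
- Keep the unstratified versions as sensitivity analyses, and state beside the sample-size text that the 75% was computed for chi-squared.
- If a sparse-data fallback is wanted, use exact CMH only when the Mantel-Fleiss criterion is not met. That happens in 0.03% to 0.05% of null trials. A rule based on any within-stratum expected count below 5 would fire in 10% to 89% of trials at 50% versus 30% (half secondary) or 83% to 100% (30% secondary), so it is unsuitable.

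**If the pivotal test cannot be changed because data have been seen,** keep the protocol's test, name it as the uncorrected Pearson chi-squared test, and add the stratified ORR, EFS and OS analyses as labelled sensitivity analyses.

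**In either case,** delete the Fisher alternative from SAP 10.1.

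**Cost.** Wording in the sections listed and a few lines of code; the factor is already used in IWRS. The statistical downside of CMH as pivotal is about 1 point of ORR power if the factor turns out not to be prognostic.
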